7.4 Control and mitigation of risks

The surgical procedure is described in the surgery guide for the Osia System⁵. The guide has been developed by the Sponsor together with a group of experienced Baha and Cochlear Implant surgeons. Although most of the surgical tools are the same as for Baha and CI implantation, there are some new tools provided. These have been validated during the surgical validation activity.

Before the enrollment of the clinical investigation site, each participating investigator will have completed surgical training using the Osia device according to the surgery guide.

MRI examinations may be performed safely with this implanted device under very specific conditions. An MRI information package is supplied with each implant for additional information regarding magnetic resonance imaging¹⁸.

Subjects enrolled in the investigation that receive the Osia System will receive an MRI card, for information to radiologists if an evaluation and planning of any MRI examination becomes necessary. Subjects that have received radiation therapy, or are planned for radiation therapy during the investigation, at the same side of the skull where the Osia System will be positioned are excluded from the investigation.

7.5 Risk-to-benefit assessment

The risks have been judged acceptable when weighed against the benefits of the intended performance of the investigational device.

8 DATA ANALYSIS

All subjects who are consented into the clinical study will constitute the intention-to-treat (ITT) population for the purposes of safety evaluation. Only subjects implanted with the Osia implant will be considered as the completed cases (CC) population and per protocol (PP).

Since the primary intent of this study is to provide preliminary safety and efficacy information, no formal hypotheses or sample size estimates were derived for this study.

Demographic and outcomes data for primary, secondary, and ancillary objectives will be tabulated individually along with group summary descriptive statistics where relevant.

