2.5 Subject Identification

To maintain confidentiality, the subject's name will not be recorded on any study document other than the informed consent form. All individuals who provide informed consent (sign the informed consent form) are considered consented into the study and will be assigned a unique identifier. A unique alphanumeric code will identify the subject throughout the course of the study. For example, CA01-OSI-0000, where:

- CA = Canada

- 01 = a sequential numeral corresponding the order in which a subject is enrolled into the study for a given study site, in this case this would correspond to the first subject recruited into the study for a particular site,
- OSI = an abbreviation for the study,
- 0000 = a unique, numeric study site identification.

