2.10 Replacement of subjects

If a subject discontinues his/her participation in the investigation, he/she will not be replaced if this discontinuation occurs after surgery is performed. If this discontinuation occurs before surgery, the subject will be replaced in order to reach up to 20 evaluable subjects.

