3.2 Objectives and outcome measures

Primary objective	Outcome measure
To quantify the type and severity of adverse events in the pediatric population implanted with the Osia system.	Information will be collected from visit 2 through visit 7 of the trial.

Secondary objectives	Outcome measures
To collect surgical information.	
 • Soft tissue thickness • Soft tissue reduction performed • Type of anesthesia • Surgery time • Bone polishing/removal at the actuator site • BI300 Implant length • Location of BI300 Implant • Surgical incision type/location
To collect information about daily use of sound processor (dependent on child's ability to report).	
 • Daily usage time • SoftWear Pad use • Choice of magnet strength
To compare the self-reported assessments of hearing outcome with the investigational device and in a preoperative hearing situation.	
 • Speech, Spatial and Qualities of Hearing Scale -12 (SSQ-12) using the investigational device at 6 months postoperatively vs. the unaided condition preoperatively. • For children unable to complete the SSQ-12: Speech Spatial Questionnaire for Parents using the investigational device at 6 months postoperatively vs. the unaided condition preoperatively.

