4.6 Soft tissue thickness

At visit 2 (start of surgery) soft tissue thickness should be measured. For the Osia System, the skin thickness should not exceed 6 mm to ensure optimal retention and

system performance. The measurement should be performed in the center of the marked coil position. For complete instruction, see the surgery guide ⁵.

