6.2 Adverse Events (AE)

6.2.1 Definitions

Term	Definition
Adverse Event (AE)	
Any untoward medical occurrence, unintended disease or injury, or untoward clinical signs (including abnormal laboratory findings) in subjects, users or other persons, whether or not related to the medical device used in the investigation.
 
NOTE 1: This definition includes events related to the investigational medical device or the comparator.
 
NOTE 2: This definition includes events related to the procedures involved.

Adverse Event of Special Interest (AESI)	
An AESI is an AE of scientific and medical concern specific to the Sponsor's product(s).
 
The reporting requirements from the investigator to the Sponsor for an AESI will be the same as the reporting requirements for an SAE.

Adverse Device Effect (ADE)	Adverse event related to the use of an investigational medical device.
Serious Adverse Event (SAE)	
Adverse event that:
 
 a. Led to death. b. Led to serious deterioration in the health of the subject, that either resulted in. c. A life-threatening illness or injury. d. A permanent impairment of a body structure or a body function. e. Led to unplanned in-patient or prolonged hospitalization. f. Medical or surgical intervention to prevent life-threatening illness or injury or permanent impairment to a body structure or a body function. g. Led to fetal distress, fetal death or a congenital abnormality or birth defect. 
NOTE: Planned hospitalization for a pre-existing condition, or a procedure required by the CIP, without serious deterioration in health, is not considered a serious adverse event.

Serious Adverse Device Effect (SADE)	Adverse device effect that has resulted in any of the consequences characteristic of a serious adverse event.
Unanticipated Serious Adverse Device Effect (USADE)	Serious adverse device effect, which by its nature, incidence, severity, or outcome has not been identified in the current version of the risk analysis report.

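### Section 8 takes safety evaluation over all consented children, while the only primary objective concerns implanted children from surgery onward; group AE percentages would be slightly understated if any consented child is never operated

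*Protocol*

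**What the plan says.** Protocol section 8 fixes the safety set: "All subjects who are consented into the clinical study will constitute the intention-to-treat (ITT) population for the purposes of safety evaluation". Section 2.5 says who is in it: "All individuals who provide informed consent (sign the informed consent form) are considered consented into the study". The next sentence of section 8 defines the implanted children as a set, under the labels completed cases and per protocol, but ties no safety analysis to it.

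Section 3.2 gives the only primary objective: "To quantify the type and severity of adverse events in the pediatric population implanted with the Osia system". Its outcome measure is described by "Information will be collected from visit 2 through visit 7 of the trial". Visit 2 is the surgery visit, as section 4.6 confirms ("At visit 2 (start of surgery) soft tissue thickness should be measured"), and the AE row of the Study Test Schedule also starts there. Section 6.2.7.1, by contrast, has AEs recorded from enrollment, which it calls Day 0.

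Section 2.10 foresees children who leave between consent and surgery: "If this discontinuation occurs before surgery, the subject will be replaced in order to reach up to 20 evaluable subjects".

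On reporting, section 8 says: "Demographic and outcomes data for primary, secondary, and ancillary objectives will be tabulated individually along with group summary descriptive statistics where relevant". It states no AE percentage and no denominator.

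**The concern.** The objective and the analysis set describe different groups. A child who signs the form and is never operated belongs to the safety set but not to the population of the objective. Under section 2.10 such a child is replaced, so both the leaver and the replacement are in the safety set.

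That child cannot have a surgical complication, an implant-site AE of special interest or an explant. Nor can the child have an adverse device effect, which section 6.2.1 defines as "Adverse event related to the use of an investigational medical device". Including the child adds one to the denominator of such a percentage and nothing to the numerator. A reader would take the result as the risk for an implanted child, and it would be too low. Safety is the study's stated aim and this is its only primary objective, so the denominator should match it.

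**Working it through.** The protocol has no figure to reproduce: section 8 says that no hypotheses or sample size were derived, and no AE rate is given.

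**Step 1. Can the two sets differ?** Consent is counted at signature (2.5). Discontinuation before surgery is foreseen and replaced (2.10). So consented = implanted + not implanted, and the second term can exceed 0.

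**Step 2. Inputs.**
- Implanted children: 20, the planned maximum (2.2, 2.10).
- k, consented but never operated: not given; assumed range 0 to 3.
- x, implanted children with an event of the kind summarised: not given; 2, 4 and 10 used as illustrations.
- For this arithmetic, every operated child is taken to have received the implant.

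**Step 3. Formula.** Implanted set: x/20. Consented set: x/(20+k). Ratio of the second to the first: 20/(20+k), whatever x is.

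**Step 4. Results.**

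| k | Factor 20/(20+k) | x = 2 | x = 4 | x = 10 |
|---|---|---|---|---|
| 0 | 1.000 | 10.0% | 20.0% | 50.0% |
| 1 | 0.952 | 9.5% | 19.0% | 47.6% |
| 2 | 0.909 | 9.1% | 18.2% | 45.5% |
| 3 | 0.870 | 8.7% | 17.4% | 43.5% |

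**Step 5. Scale.** The exact (Clopper-Pearson) 95% interval is 5.7 to 43.7% for 4/20 and 5.0 to 38.8% for 4/23. The shift at k = 3 is 20.0 − 17.4 = 2.6 percentage points, far inside either interval. With no events, the one-sided 95% upper bound 1 − 0.05^(1/n) is 13.9% for n = 20 and 12.7% for n = 22, so two children never exposed would lower the bound by 1.2 points.

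**Step 6. Which summaries are affected?** The factor applies exactly to AEs counted from visit 2 and to surgery- or device-related AEs, because a never-operated child contributes none. It does not apply exactly to all-cause AEs counted from enrollment under 6.2.7.1: a child who leaves before surgery can have such an event and enter the numerator. The size of the effect therefore depends partly on which AE start point governs, and 3.2 and 6.2.7.1 disagree on that. Individual listings and plain counts do not change under either.

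**The case against.** The strongest reply is that the text can be read coherently. Since 6.2.7.1 records AEs from enrollment, some set has to hold events that occur before surgery, and the consented set does this. It need not be the denominator of every device rate. Section 3.2 speaks of implanted children, section 8 defines the implanted set in its next sentence, and section 2.10 does not treat early leavers as evaluable. With at most 20 children listed individually, any percentage can be recomputed, and a SAP could set table denominators.

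Much of this stands. The harm needs both k > 0 and percentages computed on the consented set, and the protocol establishes neither. But no passage limits the consented set to holding pre-surgery events. Section 8 assigns it to safety evaluation without qualification. The denominator is therefore not simply left open for a SAP: the protocol names a set, and that set does not match the objective. The need to keep pre-surgery events is met by a separate listing.

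Three stronger readings are tempting and unsupported. A reader might infer that the published AE rates will be biased; section 8 promises group summaries only where relevant and states no percentage. A reader might infer that every AE percentage falls; all-cause AEs from enrollment need not. A reader might also infer that procedure-related AEs require their own denominator of surgeries begun. The protocol defines no such set and gives no number of surgeries begun without an implant, so that is optional.

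**Conclusion.** The mismatch is real and stands in the current text, but it is minor. If k children are consented and never operated, AE percentages from visit 2 and surgery- or device-related percentages on the consented set are understated by the factor 20/(20+k): none at k = 0, and about 5% to 13% in relative terms for k = 1 to 3. This rests on 20 implanted children, on an assumed k, and on group percentages being computed on the set section 8 names. The effect is small against sampling error, can be undone from the individual tabulations, and bears on no test or threshold. It merits correction because it concerns the only primary objective, can only make these risks look smaller, and costs little to remove.

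**What to change.** In section 8:

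1. State that the primary AE summary (all AEs from visit 2, including device-related AEs, implant-site AEs of special interest and explants) uses as denominator all children who received the Osia implant, including any later explanted.
2. List separately the AEs of consented children who did not receive an implant, including any in whom surgery was begun, and all AEs that occurred before surgery.
3. Reconcile the AE start point in section 3.2 (visit 2) with that in section 6.2.7.1 (enrollment, Day 0). The Study Test Schedule places time 0 at surgery, so the day numbering needs the same check.

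A separate denominator of surgeries begun may be added but is not needed. Calling the completed-cases set the implanted set is a wording matter only; it would avoid a clash with section 2.7, which defines completion by the assessments through 12 months.

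Cost: a few sentences and one extra listing, with no added visits or children. The AE percentages may look slightly less favourable.

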9 STATEMENT OF COMPLIANCE

9.1 Ethical requirements for the conduct of the investigation

The investigation will be conducted in accordance with the ethical principles as described in the latest version of the Declaration of Helsinki adopted by the World Medical Association.

The Clinical Investigation Plan (CIP), the informed consent form and any other written information that will be given to subjects will be submitted to the appropriate ethics committee and institutional review board.

The investigation shall not begin until approval/favorable opinion from ethics committee (EC) and institutional review board (IRB) has been obtained.

9.2 Regulatory requirements for the conduct of the investigation

The investigation involves devices that are not regulatory approved in the EU, Canada or US, (not received CE mark or 510k clearance/PMA approval), therefore the investigation needs approval from the appropriate regulatory authorities.

The investigation shall not begin until approval/favorable opinion from the regulatory authorities has been obtained.

The investigation will be conducted in accordance with applicable local regulations, e.g., data protection legislation.

9.3 Updates

The appropriate ethics committees, institutional review board, and competent authorities shall, after initial approval of the investigation, receive the following information:

- Status reports and written summary of the investigation as required.
- Documentation required in order to apply for an extension.
- Documentation required in order to apply for an amendment to the CIP or the informed consent form.
- Report(s) with new information that may affect the safety of the subjects or the conduct of the study.

A protocol amendment must be approved by concerned ethics committees, institutional review board, and competent authorities.

9.4 Quality standards

The staff at the investigational site and the Sponsor shall follow the guidelines provided in the ISO standard 'Clinical investigation of medical devices for human subjects – Good clinical practice ¹⁹.'

10 ADMINISTRATIVE ASPECTS

10.1 Training

The Sponsor will organize a Site Initiation and Training visit where the handling of the medical device(s), the CIP, investigational procedures including the informed consent process, instructions regarding case report form completion and any other matters relating to running the investigation at the site will be discussed with the investigators and queries clarified.

The principal investigator will ensure that appropriate training relevant to the investigation is given to the medical, nursing, and other staff involved at the clinic and that new information of relevance to the performance of this investigation is forwarded to the staff involved.

Each Investigator performing the surgery in the clinical investigation will be trained in the surgical procedures for the investigational device.

10.2 Investigational data

10.2.1 Case report form

Data collection will be done using a combination of paper case report forms (CRFs) and electronic data capture (EDC) system. Specific training and instruction on how to complete the CRFs and enter the data into the EDC will be provided to the investigator and other site staff according to the delegation log. Upon request by the investigator, the Sponsor may transfer data collected on the paper CRF by the investigational site to the EDC under special circumstances such as during EDC maintenance or system updates. Completed eCRFs within the EDC will be reviewed and signed off by an investigator prior to the completion of the trial.

10.2.2 Source data

Defined as all the information in original records, certified copies of original records of clinical findings, observations, or other activities in a clinical investigation, necessary for the reconstruction and evaluation of the clinical investigation.

10.2.3 Data management

All study data will be entered into an Electronic Database Capture (EDC) system. Study personnel requiring access will have their own Login/Password. Access to clinical study information will be based on an individual's role and responsibilities. The application

provides hierarchical user permission for data entry, viewing, and reporting options. For optimum security, all communications between the users and the EDC operate on a secured socket layer (SSL) using 256-bit encryption. The web servers are protected by a managed firewall from potential web and network attacks and the network is guarded by an intrusion detection and protection surveillance system against malicious threats.

This application is designed to be in full compliance with International Conference on Harmonization and Good Clinical Practices (ICH-GCP), FDA CFR 21 Part 11 Electronic Record and Electronic Signatures, the FDA's "Guidance: Computerized Systems Used in Clinical Trials (May 2007), and the Privacy Rule of the Health Insurance Portability and Accountability Act of 1996 (HIPAA)."

As part of the data entry and validation process, the data stored in the EDC is checked against the source data, and also against edit check queries to confirm that the data received is within expected ranges. If any data is missing or is outside of expected limits, a query is created and sent to the site coordinator so that data may be verified and corrected. All changes made to a form are stored in an audit trail.

10.2.4 Record Keeping and Retention

Data generated for the study should be stored in a limited-access file area and be accessible only to representatives of the study site, the Sponsor and its representatives, and FDA/relevant health authorities/regulatory agencies. All reports and communications relating to study subjects will identify subjects only by subject unique identification code. Complete subject identification will be kept by the Investigator. This information will be treated with strict adherence to professional standards of confidentiality.

An Investigator must in reasonable time, upon request from any properly authorized officer or employee of FDA/relevant health authority or regulatory agency, permit such officer or employee to have access to requested records and reports, and copy and verify any records or reports made by the Investigator. Upon notification of a visit by a regulatory authority, the Investigator will contact the Sponsor or its designee immediately. The Investigator will also grant Sponsor representatives the same privileges offered to relevant health authority or regulatory agents/officers/employees.

The Investigator must provide the Sponsor or its designee with the following documents at the time of site qualification and prior to study initiation and retain a copy in the site study file:

- Signed and dated curriculum vitae for the Principal Investigator.
- A copy of the original approval for conducting the study by the Ethics Committee. Renewals, with continuance of the study, must be submitted at yearly intervals or as required by policy and a copy of the approved and dated renewal provided to the Sponsor.
- A copy of the approved informed consent form along with any modifications initiated by the Sponsor over the course of the study.
- An Ethics member list and Federal Wide Assurance (FWA) Number.

- A signed Financial Disclosure Form for each Investigator.
- An Investigator Agreement for this protocol signed and dated by each Investigator.

In addition to the documents listed above, the study site will also retain the following items and make them available for Sponsor review upon request.

- Certifications, applicable study equipment (audiometers, etc.) calibration records and laboratory reference ranges for all local laboratories used for this study. The Sponsor will verify all equipment requirements at the study qualification and/or initiation. Sites with outdated and/or non-compliant equipment will either not be approved for study participation or will be advised to discontinue study-related activities should non-compliance be noted during regular study monitoring visits.
- All original informed consent forms with required signatures.
- All Ethics correspondence (i.e., informed consent [including any approved revisions], protocol, AEs, advertisements, newsletters).
- Copy of the Study Monitoring Log Sheet.
- Clinical and non-clinical supply shipment forms and device accountability logs.
- Copies of all correspondence pertaining to the study between Sponsor and the site.
- Copies of all SAEs reports submitted to the Sponsor.
- Copies of all Health Canada progress reports submitted to the site by the Sponsor.
- Site Delegation Signature Log.

10.2.5 Archiving

All study-related records must be maintained for at least 2 years after a marketing application (PMA) is approved for the study device; or if the application is not approved, until at least 2 years after shipment and delivery of the last device for investigational use is discontinued and FDA/health authorities or regulatory agencies have been notified of study closure. The Sponsor will notify the principal Investigator when records are no longer needed. The Investigator will not discard any records without notifying the Sponsor. If the Principal Investigator moves from the current investigational site, the Sponsor should be notified of the name of the person who will assume responsibility for maintenance of the records at the investigational site or the new address at which the records will be stored. The Investigator will notify the Sponsor as soon as possible in the event of accidental loss or destruction of any study documentation.

